9.2.4. Treatment Given as a Result of the Event

The event impact in terms of treatment provided will be as either: none, medication administered, non-drug therapy administered, surgery performed, hospitalization, or other (with a specification).

9.2.5. Outcome Assessment

The outcome of the event will be assessed as either: fatal, not recovered/not resolved, recovered/resolved, recovered/resolved with sequelae, recovering/resolving, or unknown. Only one AE per subject is allowed to have an outcome assessment as "death." If there are multiple causes of death for a given subject, only the primary cause of death will have an outcome of death.

9.3. SERIOUS ADVERSE EVENTS

A SAE is defined as any AE that:

- Results in death
- Is life threatening (the subject is at immediate risk of dying from the adverse experience)
- Requires subject's hospitalization or prolongs existing hospitalization
- Results in persistent or significant disability/incapacity
- Is a congenital anomaly/birth defect

[figure not shown]
CONFIDENTIAL Page 77 of 101

• Important medical events that may not result in death, be life-threatening, or require hospitalization may be considered a serious adverse effect when, based upon appropriate medical judgment, they may jeopardize the subject or subject and may require medical or surgical intervention to prevent one of the outcomes listed in this definition.

9.4. REPORTING OF SERIOUS ADVERSE EVENTS (SAE)

The Investigator is required to report all SAEs that occur during the time period specified in Section 9.2. Once the Investigator becomes aware of an SAE, he/she must report the SAE to Medical Monitor within 24 hours.

The Medical Monitor may request additional supporting documentation as it becomes available, such as lab reports, ECG reports, discharge summary, hospital notes, etc, if applicable. Additional follow-up information as it becomes available must be reported to the Medical Monitor.

The Investigator is also responsible for reporting all SAEs to the appropriate Institutional Review Board (IRB) in accordance with local laws and regulations. The Investigator is responsible for maintaining documentation in the study file that indicates the IRB has been properly notified.

[figure not shown]
9.5. SAE FOLLOW-UP

All subjects experiencing an SAE, including the discontinued subjects, must be closely followed until sufficient information is obtained to indicate a return to normal status or until the event stabilizes at a level acceptable to the investigator (i.e., recovery, return to baseline status, no further improvement expected, or death).

For each SAE indicated as an unresolved event on the initial report, regardless of whether the subject completed the study or withdrew, the site should submit a follow-up report with updated information.

Study participants should be instructed to notify the investigator and discontinue investigational product immediately if they become pregnant at any time during the study or if they become pregnant within 30 days of last investigational product dose. A participant whose partner has become pregnant or suspects she is pregnant during the study must report the information to the investigator. The Investigator is required to report any notification of pregnancy to CytoDyn, Inc/designated CRO promptly. The participants should receive appropriate monitoring and care

CONFIDENTIAL Page 78 of 101

until the conclusion of the pregnancy. Any complication experienced through the end of the pregnancy should be considered as an adverse event (AE), and should be recorded, and if it meets the seriousness criteria, it must be reported to CytoDyn, Inc/designated CRO promptly. Pregnancy outcomes will be reported in the clinical study report.

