This is a Phase 2, two-arm, randomized, double blind, placebo controlled multicenter study to evaluate the safety and efficacy of leronlimab (PRO 140) in patients with prolonged symptoms caused by COVID-19. Patients will be randomized to receive weekly doses of 700 mg leronlimab (PRO 140), or placebo. Leronlimab (PRO 140) and placebo will be administered via subcutaneous injection.

The study will have three phases: Screening Period, Treatment Period, and Follow-Up Period.

Screening Period (up to 1 week):

Screening assessments will commence at Visit 1 (V1) after obtaining signed informed consent, and will include review of medical and medication history, eligibility evaluation, vital signs, pulse oxygen saturation, physical examination, electrocardiogram (ECG), clinical symptom score assessment, and laboratory sample collection for routine serum biochemical, hematologic, coagulation, urinalysis, and urine pregnancy (if applicable). These assessments must be conducted within 7 days of the First Treatment Visit (V2).

All subjects who fail to meet eligibility criteria are considered screen failures, and are exited from the study without further evaluation.

Treatment Period (56 Days± allowed windows):

The schedule of visits during Treatment Period is as follows:

- Visit 2 (V2) [first treatment]: Within 1 week of the Screening Visit
- Visit 3 (V3): 3 (±1) days after V2
- Visit 4 (V4) [second treatment]: 7 (±1) days after V2
- Visit 5 (V5): 3 (±1) days after V4
- Visit 6 (V6) [third treatment]: 7 (±1) days after V4
- Visit 7 (V7): 3 (±1) days after V6
- Visit 8 (V8) [fourth treatment]: 7 (±1) days after V6
- Visit 9 (V9): 3 (±1) days after V8
- Visit 10 (V10) [fifth treatment]: 7 (±1) days after V8
- Visit 11 (V11): 3 (±1) days after V10

CONFIDENTIAL Page 7 of 101

Name of Sponsor/Company:		
CytoDyn, Inc.		
Name of Study Product:		
Leronlimab (PRO 140)		
Protocol Number: Indication:		
CD15_COVID-19	Coronavirus Disease 2019 (COVID-19)	

- Visit 12 (V12) [sixth treatment]: 7(±1) days after V10
- Visit 13 (V13): 3 (±1) days after V12
- Visit 14 (V14) [seventh treatment]: 7(±1) days after V12
- Visit 15 (V15): 3 (±1) days after V14
- Visit 16 (V16) [eighth treatment]: 7(±1) days after V14
- Visit 17 (V17) / End of Treatment (EOT) Visit: 7 (±1) days after V16.

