1.4. SUMMARY OF PRIOR PRE-CLINICAL AND CLINICAL STUDIES

1.4.1. Pre-Clinical Studies with PRO 140

In vitro and *in vivo* preclinical studies have been conducted to determine the pharmacokinetic, immunogenicity, and toxicity profiles of leronlimab (PRO 140) following IV and SC administration. Several acute and chronic toxicity studies have been conducted to support the clinical development plan.

Acute toxicity of leronlimab (PRO 140) was evaluated in New Zealand rabbits, following IV administration of 5 or 15 mg/kg. Chronic toxicity was evaluated in cynomolgus monkeys following biweekly administration of IV doses up to 10 mg/kg for six months and biweekly administration of various SC doses up to 50 mg/kg for 24 weeks. The drug was generally well tolerated. Biweekly administration of IV doses up to 10 mg/kg for six months resulted in minimum to mild lymphoid hyperplasia in assorted lymph nodes and spleen, which was considered an expected immune response to a foreign protein. Biweekly administration of SC doses up to 50 mg/kg for 24 weeks resulted in minimum injection-site reactions (minimal, multifocal, mononuclear cell infiltrates in the subcutis), which were considered due to an inflammatory response to the injected antigen. Monkeys tolerated treatment with leronlimab (PRO 140) for 24 weeks without evidence of local or systemic toxicity. Leronlimab (PRO 140) caused no mortality, cageside observations, in-life injection-site observations, or gross pathologic findings. Chronic treatment with leronlimab (PRO 140) did not affect body weight, food consumption, hematology, clinical chemistry or coagulation parameters.

CONFIDENTIAL Page 23 of 101

Both IV and SC administration resulted in elimination half-lives of approximately 200 hours, and overall exposure increased with increasing doses. Following SC administration of leronlimab (PRO 140) in monkeys, the maximal concentration (C_{max}) was achieved within 56 hours and bioavailability for leronlimab (PRO 140) after SC dosing was approximately 70%.

1.4.2. Clinical Studies with PRO 140

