1.6. RISKS / BENEFITS ASSESSMENT

Allergic Reaction

Leronlimab (PRO 140) belongs to the monoclonal antibody class of drugs. Monoclonal antibodies are sometimes associated with allergic reactions or flu-like reactions (such as fever, chills, and aches) or injection-site reactions. These events are usually of short duration if they occur at all. Severe allergic reactions, however, can be life-threatening. Although anaphylaxis has not been observed in prior trials of leronlimab (PRO 140), the protein infusion always carries theoretical risk for anaphylactic shock. Accordingly, whenever leronlimab (PRO 140) is administered to subjects, procedures should be available and in place to manage the occurrence of anaphylactic shock.

Immune Response

People who take leronlimab (PRO 140) or other monoclonal antibodies can also develop an immune response to leronlimab (PRO 140) that may affect their ability to receive monoclonal antibodies, or to benefit from diagnosis or therapy with a monoclonal antibody in the future.

Pregnancy

Risks to unborn babies exposed to leronlimab (PRO 140) are unknown at this time; thus pregnant females will be excluded from this study. Females of childbearing potential must have a negative pregnancy test prior to enrollment. Both male and female patients and their partners of childbearing potential must agree to use appropriate birth control methods throughout the study duration (excluding women who are not of childbearing potential and men who have been sterilized).

Venipuncture

Blood sampling is required as part of the study protocol. Blood sampling carries a minimal risk of minor discomfort and the possibility of minor bruising at the site of the needle puncture and, rarely, the possibility of infection at the needle puncture site.

Unknown Risks

As with all research, there is the remote possibility of risks that are unknown or that cannot be foreseen based on current information.

Theoretical risk for increased severity of West Nile virus infection

Individuals who lack a functional CCR5 gene are at increased risk for severe infection by West Nile virus [Thompson, 2009]. Because of this, treatment with CCR5 co-receptor antagonists poses a theoretical risk for increased severity of West Nile virus infection. However, this concern is mitigated by several factors. First, no increased risk was observed for individuals who possess one functional and one non-functional CCR5 gene, indicating that an intermediate amount of

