- 6. Men and women of childbearing potential and their partner must agree to use two medically accepted methods of contraception (e.g., barrier contraceptives [male condom, female condom, or diaphragm with a spermicidal gel], hormonal contraceptives [implants, injectables, combination oral contraceptives, transdermal patches, or contraceptive rings], or one of the following methods of birth control (intrauterine devices, bilateral tubal occlusion, or vasectomy) or must practice complete sexual abstinence for the duration of the study (excluding women who are not of childbearing potential and men who have been sterilized).
- 7. Females of child-bearing potential must have a negative urine pregnancy test at Screening Visit and prior to receiving the first dose of study drug; and Male participants must agree to use contraception and refrain from donating sperm for at least 90 days after the last dose of study intervention.
- 8. Subject is willing and able to comply with scheduled visits, drug administration plan, laboratory tests, other study procedures and study restrictions

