3.3.2. Exclusion Criteria

Potential subjects meeting any of the following criteria will be excluded from enrollment:

- 1. Exhibiting signs of moderate or severe pulmonary disease (such as COPD, asthma, or pulmonary fibrosis)
- 2. Ongoing requirement of oxygen therapy
- 3. Pulse oxygen saturation (SpO2) of <94% on room air at the time of screening
- 4. History of splenectomy
- 5. Liver cirrhosis or patient showing signs of clinical jaundice at the time of screening
- 6. Chronic kidney disease stage 4 or requiring dialysis at the time of screening

CONFIDENTIAL Page 42 of 101

- 7. NYHA Class III or IV congestive heart failure (CHF)
- 8. Exhibiting signs of uncontrolled hypo-or hyper- thyroidism at the time of Screening
- 9. Uncontrolled rheumatologic disorders at the time of screening
- 10. History of organ transplantation or are candidates for organ transplantation at the time of screening
- 11. History of Chronic Fatigue Syndrome prior to COVID19 infection
- 12. History of fibromyalgia prior to COVID-19 infection
- 13. History of major psychiatric disorder including bipolar disorders, schizophrenia, schizoaffective disorder, major depression. Patients with major depression can be enrolled if patient has had no episode within the past year or is considered in remission or controlled by treatment.
- 14. Any malignancy within the past 5 years, excluding successfully treated basal cell carcinoma or squamous cell carcinoma without evidence of metastases.
- 15. Any other clinically significant serious systemic diseases which would interfere with study conduct or study results interpretation per the Investigator.
- 16. Treatment with immunosuppressive or immunomodulatory medications within 5 half-lives prior to screening. Patients on replacement therapy for adrenal insufficiency will be allowed. Patients on stable (> 3 months) low dose corticosteroid ≤ 5 mg Prednisone will be allowed.
- 17. History of allergic reactions attributed to compounds of similar chemical or biologic composition to leronlimab (PRO 140) are not eligible
- 18. Ongoing use of CCR5 antagonist
- 19. Inability to provide informed consent or to comply with test requirements
- 20. Consideration by the investigator, for safety reasons, that the subject is an unsuitable candidate to receive study treatment
- 21. Pregnancy or breast feeding
- 22. Participating in another study for an investigational treatment

CONFIDENTIAL Page 43 of 101

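### The duty to report a partner's pregnancy stops with the study, 31–39 days after the last dose for an on-schedule completer, while male contraception is required for 90 days

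*Combined protocol and SAP*

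**What the plan says.** Section 9.5 of the protocol has two reporting rules. For partners: "A participant whose partner has become pregnant or suspects she is pregnant during the study must report" the information to the investigator. No period after the last dose is attached. For participants themselves, the duty covers pregnancy during the study, "or if they become pregnant within 30 days of last investigational product dose". The investigator must then pass on any pregnancy of which notice is received, the pregnancy is followed to its conclusion, and outcomes go into the clinical study report.

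Contraception is covered in three places:

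- Section 3.3.1, item 7: "Male participants must agree to use contraception and refrain from donating sperm for at least 90 days after the last dose of study intervention".
- Section 3.3.1, item 6: two methods of contraception, or abstinence, for men and women of childbearing potential. The only period named is the duration of the study.
- Section 1.6: patients of both sexes and their partners "must agree to use appropriate birth control methods throughout the study duration".

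Section 5.1 treats a subject as having completed once the follow-up visit assessments are done, which is V18. Section 9.2 runs adverse event reporting from the first treatment visit to the final study visit.

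**The concern.** Section 1.6 says that the risk to an exposed unborn child is not known. The protocol asks men for precautions for 90 days after dosing, yet drops the duty to report a partner's pregnancy when the man leaves the study, which is well before day 90. During the remaining days the precaution is in force, but the event it is meant to prevent need not be reported.

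Capture of partner pregnancies depends on this instruction. Partners are not tested, and adverse event reporting closes at the final visit. Section 9.5 promises pregnancy outcomes in the study report, and SAP Section 8.3.7 plans a listing of pregnancy data. Both would cover the uncovered days only as far as men volunteer information they have not been asked to give.

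The contraception periods also need reconciling. Item 7 goes beyond the study for men, while Section 1.6 stops at the study duration for everyone.

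**Working it through.** The documents state neither the interval from last dose to study end nor the gap. Both follow from the schedule.

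**Inputs**

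- Last dose. Synopsis, Trial Design: "Visit 16 (V16) [eighth treatment]: 7(±1) days after V14" (nominal Day 49).
- Last dose to end of treatment. Same list: "Visit 17 (V17) / End of Treatment (EOT) Visit: 7 (±1) days after V16", so 6–8 days.
- End of treatment to V18. Section 4.3 and Table 4-2: 28 (±3) days, so 25–31 days (nominal Day 84).
- Male contraception period. Section 3.3.1, item 7: a minimum of 90 days from the last dose.
- Assumption: for one man, the study ends at V18 if he completes (Section 5.1), or when he leaves it.

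**Step 1. Last dose to study end, dosed at V16 and completing in window**

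- Shortest: 6 + 25 = 31 days
- Longest: 8 + 31 = 39 days
- Nominal: 84 − 49 = 35 days

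**Step 2. Part of the 90 days with no duty to report a partner's pregnancy**

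- Smallest: 90 − 39 = 51 days (51/90 = 57%)
- Largest: 90 − 31 = 59 days (59/90 = 66%)
- Nominal: 90 − 35 = 55 days

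**Step 3. Only the V16 dose missed, all visits kept**

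The last dose is then at V14, one further 6–8 day interval earlier.

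- Study end: 6 + 6 + 25 = 37 to 8 + 8 + 31 = 47 days after the last dose
- Gap: 90 − 47 = 43 to 90 − 37 = 53 days

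**Step 4. A man who leaves the study on the day of his last dose**

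- Gap: up to 90 − 0 = 90 days

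**Step 5. The 30-day clause for participants' own pregnancies**

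- It ends 31 − 30 = 1 to 39 − 30 = 9 days before V18 for an on-schedule completer, so it adds nothing to the cover already given during the study.
- For a woman who withdraws early it can run past her last visit, and there it does add cover.

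**The case against.** **What stands on the other side.** Section 9.5 puts no time limit on the investigator's duty to forward a pregnancy once told of it, or on following it to its conclusion. A late partner pregnancy that is volunteered is therefore captured. Only the man's duty to volunteer it has no post-dose period. A reader might infer that pregnancies in the gap go unreported or will be missing from the study report. The documents support only that reporting them is not required.

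**The 90 days.** A reader might infer that the protocol regards male exposure as a fetal risk for 90 days. Item 7 gives no reason for its period, so this is an inference. Nor does any section say that reporting and contraception periods must match. The argument for aligning them is coherence and cheap safety capture.

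**The contraception conflict.** Items 6 and 7 both apply to men, so the longer period can be read as governing. The study-duration phrase in item 6 can be read as attached to abstinence alone. The mismatch may therefore be a matter of wording, but Section 1.6 still states a shorter period for men than item 7.

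**Half-lives.** A reader might infer that reporting always ends before five half-lives. Section 1.4.1 gives "elimination half-lives of approximately 200 hours", and exclusion 16 applies a washout of "within 5 half-lives prior to screening"; 5 × 200 / 24 = 41.7 days, against a study end at 31–39 days. The documents do not support this. The half-life is from monkeys, exclusion 16 concerns other drugs before screening, and with only the V16 dose missed V18 falls at 37–47 days, which can exceed 41.7. The point does not rely on it.

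**Women.** A reader might carry the 90 days over to participants' own pregnancies. No section gives women a contraception period after the study, so that extension has no basis in the documents.

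**Scale and unseen material.** With 50 subjects randomized 1:1, about 25 receive the drug, and only the men among them can contribute an exposed partner pregnancy. Few events are likely. The consent pages and the pregnancy forms named in the SAP are not available here and might instruct men further.

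**Conclusion.** The point holds for partner pregnancies. Section 9.5 sets no post-dose reporting period for them, while item 7 requires precautions for at least 90 days from the last dose, and no other section of the protocol or SAP closes the gap. For a man dosed at V16 who completes in window, 51–59 of the 90 days (57–66%, nominally 55 days) carry no duty to report. The figure is 43–53 days if only the V16 dose is missed, and up to 90 days for a man who leaves at his last dose.

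The result rests on the visit windows as written, on reading the study as ending for each man at V18 or at his withdrawal, and on the 90 days in item 7 as it now stands. If the sponsor settles on another period, the gap changes with it. The 30-day clause is redundant for women who complete on schedule, but not for those who withdraw early.

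This is an inexpensive improvement to safety capture that should be made. Given the trial's size, it is not a major defect.

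**What to change.** - Reconcile Sections 1.6, 3.3.1 (items 6 and 7) and 9.5, so that the contraception period for each sex is stated once and consistently. Which period is right is for the sponsor to decide.
- In Section 9.5, give partner pregnancies an explicit reporting window. Count it from the last dose, apply it to men who withdraw early as well as to completers, and make it at least as long as the male contraception period settled on.
- Align the window for a participant's own pregnancy with whatever post-dose contraception period applies to her.
- Collect late reports by telephone from the subject, with no added visit, and put the same instruction in the consent form.

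The cost is protocol and consent wording, plus a pregnancy log that stays open about two months longer: 51–59 days past V18 for an on-schedule completer if the 90 days are kept.

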9.6. EXPECTED/ANTICIPATED EVENTS

Refer to Investigator Brochure for the expected/anticipated events.

CONFIDENTIAL Page 79 of 101

10. DIRECT ACCESS TO SOURCE DATA/DOCUMENTATION

Subjects will be identified on eCRFs by a unique subject identification number and on source documents by name and date of birth. No personal identifier will be used in any publication or communication used to support this research study. The subject identification number will be used if it becomes necessary to identify data specific to a single subject.

The local IRB, FDA and other global regulatory authorities, the monitors, auditors and personnel authorized by the Sponsor are eligible to review the medical and research records related to this study as part of their responsibility to protect human subjects in clinical research. They will be given direct access to source data and documentation (e.g., medical charts/records, printouts etc.) for source data verification, provided that subject confidentiality is maintained in accordance with local requirements. Access to electronic medical records may be governed by institution policy and each site will be required to ensure access while remaining compliant with institutional requirements.

CONFIDENTIAL Page 80 of 101

11. QUALITY CONTROL AND QUALITY ASSURANCE

11.1. MONITORING REQUIREMENTS

The specific obligations outlined in 21 Code of Federal Regulations (CFR) and ICH guidelines require the Sponsor to maintain current personal knowledge of the progress of a study. Therefore, the Sponsor's designated monitor will visit the site during the study as well as maintain frequent telephone and written communication. The Investigator will permit the Sponsor to monitor the study as frequently as is deemed necessary and provide access to medical records to ensure that data are being recorded adequately, that data are verifiable and that protocol adherence is satisfactory.

As delineated above, the Investigator will permit representatives of the Sponsor and/or designated CRO to inspect all CRFs and corresponding study subject original medical records (source documents) at regular intervals throughout the study. Subject original medical records and other relevant data must be available to support all data recorded in the eCRF. In addition to the original medical records, these data may include but are not limited to study, laboratory reports, etc.

In accordance with federal regulations, site inspections will serve to verify strict adherence to the protocol and the accuracy of the data that is being entered on the case report forms. A Monitoring Log will be maintained at each study site. The Monitoring Log will be signed by the monitor, dated and stated the type of visit. The Investigator should be aware that the study site and subject records may be inspected by the Sponsor and or representatives of the designated CRO, FDA or other regional regulatory authority.

